7.2.1 Primary Efficacy Endpoint

The primary efficacy endpoint is the change from baseline in mean monthly migraine days across the 12-week treatment period. Baseline is defined as the number of migraine days during the last 28 days prior to the randomization date.

7.2.2 Secondary Efficacy Endpoints

The Secondary Efficacy Endpoints for all regions except Europe and Canada:

- Change from baseline in mean monthly headache days across the 12-week treatment period
- Change from baseline in mean monthly acute medication use days across the 12-week treatment period
- At least a 50% reduction in 3-month average of monthly migraine days
- Change from baseline in MSQ v2.1 Role Function-Restrictive domain score at Week 12
- Change from baseline in mean monthly Performance of Daily Activities domain score of the AIM-D across the 12-week treatment period.
- Change from baseline in mean monthly Physical Impairment domain score of the AIM-D across the 12-week treatment period.

The Secondary Efficacy Endpoints for Europe and Canada:

- Change from baseline in mean monthly headache days across the 12-week treatment period
- Change from baseline in mean monthly acute medication use days across the 12-week treatment period
- At least a 50% reduction in 3-month average of monthly migraine days
- Change from baseline in the HIT-6 total score at Week 12
- Change from baseline in MSQ v2.1 Role Function-Restrictive domain score at Week 12

7.2.3 Additional Efficacy Endpoints

Additional efficacy endpoints for the United States and Europe are provided below. Related analysis will be documented in the statistical analysis plan (SAP).

- $\geq 25\%$, $\geq 30\%$, $\geq 50\%$, $\geq 75\%$, 100% improvement (decrease) in monthly migraine days at Weeks 1 to 4, 5 to 8, and 9 to 12
- $\geq 25\%$, $\geq 30\%$, $\geq 75\%$, 100% improvement (decrease) in 3-month average of monthly migraine days
- Change from baseline in monthly migraine days at Weeks 1 to 4, 5 to 8, and 9 to 12
- Change from baseline in monthly headache days at Weeks 1 to 4, 5 to 8, and 9 to 12
- Change from baseline in monthly cumulative headache hours at Weeks 1 to 4, 5 to 8, 9 to 12, and average across the 12-week treatment period
- Change from baseline in monthly acute medication use days at Weeks 1 to 4, 5 to 8, and 9 to 12
- Change from baseline in monthly triptan use days at Weeks 1 to 4, 5 to 8, 9 to 12, and average across the 12-week treatment period
- Change from baseline in monthly moderate/severe headache days at Weeks 1 to 4, 5 to 8, 9 to 12, and average across the 12-week treatment period
- Change from baseline in monthly severe headache days at Weeks 1 to 4, 5 to 8, 9 to 12, and average across the 12-week treatment period
- Change from baseline in weekly migraine days at Weeks 1-4

- Participant having a migraine day on the day of initial dose and on each day of the 6 days post the initial dose.
- Change from baseline in the HIT-6 total score at Weeks 4, 8, and 16 (for Europe and Canada)
- Change from baseline in the HIT-6 total score at Weeks 4, 8, 12, and 16 (for all regions except Europe and Canada)
- At least a 5-point improvement (decrease) from baseline in HIT-6 total score at Weeks 4, 8, 12, and 16
- Participant assessed by the PGIC as “much better” or “very much better” at Week 12
- Participant reporting “satisfied” or “extremely satisfied” with study medication for migraine prevention at Weeks 4, 8, and 12
- Change from baseline in percent work time missed, percent impairment while working, percent overall impairment, and percent activity impairment due to migraine at Weeks 4, 8, and 12 as assessed by the WPAI:MIGRAINE
- Change from baseline in the MIDAS total score at Week 12
- Change from baseline in MIDAS absenteeism score (Questions 1, 3, and 5) at Week 12
- Change from baseline in MIDAS presenteeism score (Questions 2 and 4) at Week 12
- Change from baseline in PGI-S score at Weeks 4, 8, and 12
- Change from baseline in the MSQ v2.1 Role Function-Restrictive domain score at Weeks 4, 8, and 16
- Change from baseline in the MSQ v2.1 Role Function-Preventive domain score at Weeks 4, 8, 12, and 16
- Change from baseline in the MSQ v2.1 Emotional Function domain score at Weeks 4, 8, 12, and 16
- Change from baseline in monthly Performance of Daily Activities domain score of the AIM-D at Weeks 1 to 4, 5 to 8, and 9 to 12
- Change from baseline in monthly Physical Impairment domain score of the AIM-D at Weeks 1 to 4, 5 to 8, and 9 to 12
- Change from baseline in mean monthly Performance of Daily Activities domain score of the AIM-D across the 12-week treatment period (for Europe and Canada only)

- Change from baseline in mean monthly Physical Impairment domain score of the AIM-D across the 12-week treatment period (for Europe and Canada only)
- Change from baseline in monthly AIM-D total score at Weeks 1 to 4, 5 to 8, 9 to 12, and average across the 12-week treatment period
- Change from baseline in monthly activity level at Weeks 1 to 4, 5 to 8, 9 to 12, and average across the 12-week treatment period
- Change from baseline in monthly activity limitation at Weeks 1 to 4, 5 to 8, 9 to 12, and average across the 12-week treatment period
- Change from baseline in PHQ-9 score at Week 12

7.2.3.1 Other Health Outcome Variables

Other health outcome endpoints are listed below. The related health outcome analyses will be documented in the health economics and outcomes research SAP.

- Change from baseline in EQ-5D-5L descriptive system index score at Weeks 1 to 2, at specified windows around Weeks 4, 6, 8, 12, and 16
- Change from baseline in the EQ-5D-5L VAS score at Weeks 1 to 2, at specified windows around Weeks 4, 6, 8, 12, and 16
- Change from baseline in PROMIS-PI total score at Weeks 4, 8, and 12

7.3 Hypothesis and Methods of Analysis

For efficacy analyses, data will be analyzed according to participants' randomization assignments, regardless of actual treatment received.

For safety data analyses, the participants will be analyzed according to actual treatment received (rather than as randomized).

7.3.1 Primary Efficacy Analyses

The primary efficacy endpoint is the change from baseline in mean monthly migraine days across the 12-week treatment period. The primary null hypothesis is that atogepant 30 mg BID and 60 mg once daily are each equally effective as placebo in mean change from baseline in mean monthly migraine days across the 12-week treatment period. The alternative hypothesis is that at least 1 of the 2 doses of atogepant has a greater effect than placebo.

The primary comparison between treatment groups will be done by an MMRM of the change from baseline. The statistical model will include treatment group, visit, region, acute migraine medications during the baseline period (medication overuse Y/N), current and past use of migraine prevention medications and the number of medications failed with unique mechanisms of action (Current Use and “failed 0 medications or failed 1 or more medication(s) with the same mechanism of action”, Current Use and “failed 2 to 4 medications with different mechanisms of action”, Past Use only and “failed 0 medications or failed 1 or more medication(s) with the same mechanism of action”, Past Use only and “failed 2 to 4 medications with different mechanisms of action”, and Never Used), and treatment group by visit interaction as categorical fixed effects. The statistical model will also include the baseline score and baseline-by-visit interaction as covariates. An unstructured covariance matrix will be used to model the covariance of within-participant repeated measurements. The Kenward-Roger approximation (Kenward 1997) will be used to estimate the denominator degrees of freedom. The analysis will be performed based on all postbaseline values using only the observed cases without imputation of missing values. Pairwise contrasts in the MMRM model will be used to make the pairwise comparisons of each atogepant dose to placebo. This is the primary analysis method for the primary efficacy endpoint in support of US filing. Only data collected during the double-blind period will be included in the analysis. Participants are always analyzed based on the treatment group assigned by randomization.

7.3.1.1 Sensitivity Analyses in Missing Data Handling

Multiple sensitivity analyses for missing data handling will be conducted and summarized below. Details of the sensitivity analyses will be provided in the SAP.

ANCOVA Model Based on 3-month Average of the Monthly Migraine Days

A supportive analysis will be performed on the primary endpoint using an ANCOVA model. The response variable for the ANCOVA model is the change from baseline in the calculated average monthly migraine days during the 12-week treatment period for each participant. The ANCOVA model includes terms for treatment, region, acute medications during the baseline period (medication overuse Y/N), current or past use of migraine prevention medications and the number of medications failed with unique mechanisms of action, and baseline score. The treatment difference for atogepant doses versus placebo will be estimated and reported along with the corresponding 95% CI and nominal p-value for superiority testing.

Within-group Imputation Based on Observed Data

Sensitivity analysis will be performed based on imputation using participants from the same treatment group with observed data under the missing at random (MAR) assumption. Missing data for participants who prematurely discontinued are assumed to copy the profile of participants in the same treatment group with observed data.

Copy-Reference Approach

Copy-reference approach will be performed on the primary endpoint to assess the robustness of the MMRM analysis to possible violation of the MAR assumption. This sensitivity analysis is one type of pattern mixture model (PMM), under which data could be missing not at random (MNAR), with repeated analyses combined via the reference based multiple imputation (MI) procedure. Participants who discontinued in the Atogepant groups are assumed to have no treatment effect after the discontinuation. Participants are assumed to copy the profile of placebo arm and missing values are imputed based on the distribution estimated from the placebo group under the MAR using copy reference approach.

MMRM Based on Primary Measures Collected During the Double-blind and Follow-up Periods

The details for this analysis are provided in Section 7.4. The primary analysis in support of EU filing will serve as one sensitivity analysis in support of US filing.

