7.6 Sample Size Calculation

A total sample size of 250 participants will be randomized per treatment group and that will provide at least 96% power to detect the treatment difference between each of the 2 atogepant doses (assumed equally effective) and placebo for the primary efficacy endpoint. The sample size of this study was selected to provide sufficient power for the first 3 secondary endpoints as shown in [Table 4](#). The power calculations are based on the following assumptions:

1) The treatment difference from placebo will be similar to the average value across the CM prevention studies for Botox ([Aurora 2010](#), [Diener 2010](#)) and TEV-48125 ([Bigal 2015](#), [Silberstein 2017](#)). In particular, the assumed treatment difference from placebo in change from baseline in mean monthly migraine days across the 12-week treatment period is -2 days, and the standard deviation is 5.5 days. Detailed treatment difference and standard deviation assumptions are listed in [Table 4](#).

2) The study statistical testing plan controls the overall type I error at 5%. The power calculations of the primary and secondary endpoints have taken the multiple comparisons into consideration by testing each dose versus placebo at a 0.025 significance level, 2-sided. Once the primary endpoint for each dose is significant at 0.025, 2-sided, the secondary endpoints will be tested sequentially. A detailed graphical multiple comparison procedure will be presented in the SAP.

Table 4 Statistical Power for Primary and the First Three Secondary Endpoints

Hypothesis Testing	Endpoint	Treatment Difference from Placebo	Standard Deviation	Statistical Power
Primary	Change from baseline in mean monthly migraine days across the 12-week treatment period	-2	5.5	96%
Secondary 1	Change from baseline in mean monthly headache days across the 12-week treatment period	-2	6.0	93% ^a
Secondary 2	Change from baseline in mean monthly acute medication use days across the 12-week treatment period	-1.8	5.5	92% ^a
Secondary 3	At least a 50% reduction in mean monthly migraine days across the 12-week treatment period	33% Placebo Rate	49% Atogepant Rate	92% ^a

^a: Statistical powers for secondary endpoints are conditional on success of prior endpoints (assuming independence among the endpoints) in the sequence for the comparisons of each dose versus placebo

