6.3 MODIFIED INTENT-TO-TREAT POPULATION

The Modified Intent-to-Treat (mITT) Population will consist of all randomized participants who received at least 1 dose of study intervention, had an evaluable baseline period of electronic diary (eDiary) data, and had at least 1 evaluable post-baseline 4-week period (Weeks 1 to 4, 5 to 8, and 9 to 12) of eDiary data during the double-blind treatment period. All efficacy analyses described in Sections 0 will be performed using the mITT population. For efficacy analyses, data will be analyzed according to participants' randomization assignments, regardless of actual treatment received.

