3. The ANCOVA analysis results from 100 completed datasets are combined for overall estimation and inference using Rubin's rule ([Rubin 1987](#)) to produce a pooled estimate of LS mean difference, its SE, and corresponding p-value for the test of null hypothesis of no treatment effect.

Copy-Reference Approach

The copy-reference approach is one type of pattern-mixture models (PMM), under which data could be missing-not-at-random (MNAR), with repeated analyses combined via the reference based multiple imputation (MI) procedure ([Carpenter et al, 2013](#)). This approach is to assess the robustness of the MMRM analysis to possible violation of the missing-at-random (MAR) assumption in the primary analysis.

Step 1. A few intermittent missing values will be imputed by the Markov Chain Monte Carlo (MCMC) at first. The MCMC imputation assumes missing-at-random (MAR) for intermittent missing data. The MCMC method will be implemented using SAS PROC MI statement "MCMC impute=monotone". This is achieved with the use of option IMPUTE = MONOTONE in the MCMC statement. Then the rest of the missing data will follow monotone missing pattern.

Step 2. Implementation of the copy-reference method are as follows:

1. The reference-based approach uses the placebo group as the reference. The missing values in the reference group are imputed using the observed data in that group under the missing-at-random assumption. The missing pattern is defined by the participant's last visit with a non-missing value. The mean vector and the covariance matrix of the multivariate normal distribution are estimated for reference group. The imputation of missing data is not based on each of the reasons of early termination, because there may not be sufficient non-missing efficacy data in each of the reason categories to serve as a stable reference.
2. For atogepant treatment groups, missing values are imputed based on the distribution estimated from the reference group (placebo group).

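### Protocol 7.3.1.1 says the copy-reference analysis assumes no effect once atogepant is stopped, but the method carries forward a correlation-weighted share of the earlier effect

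*Protocol*

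**What the plan says.** Under Copy-Reference Approach, Protocol 7.3.1.1 gives the assumption as: "Participants who discontinued in the Atogepant groups are assumed to have no treatment effect after the discontinuation". It then names the method: "missing values are imputed based on the distribution estimated from the placebo group under the MAR using copy reference approach".

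SAP 10.2.1.1 gives the implementation. Intermittent gaps are filled first by MCMC. Dropout patterns are then set by the last visit with data. For placebo, "The mean vector and the covariance matrix of the multivariate normal distribution are estimated for reference group". For the active arms, "For atogepant treatment groups, missing values are imputed based on the distribution estimated from the reference group (placebo group"). There are 100 imputations, an ANCOVA on the three-month average, and pooling by Rubin's rule. The SAP does not repeat the protocol's sentence about zero effect.

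These analyses use the mITT population, whose members "had at least 1 evaluable post-baseline 4-week period (Weeks 1 to 4, 5 to 8, and 9 to 12) of eDiary data during the double-blind" phase (SAP 6.3). Every participant with an imputed month therefore has at least one observed month.

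**The concern.** Imputing from the placebo distribution is not the same as assuming zero effect after stopping. Copy reference treats an atogepant dropout as a placebo participant throughout, including while on drug. If month 1 was better than placebo, the method reads that as a favourable placebo residual and carries it forward through the placebo covariance. The protocol's sentence describes a different assumption: benefit up to discontinuation, none afterwards.

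What is at stake is the meaning of the robustness claim. The within-group imputation is missing at random (MAR). The ANCOVA on the three-month average lets dropouts keep their on-treatment mean. No jump-to-reference, delta-adjusted or tipping-point analysis is planned. A report that followed the protocol's wording could claim robustness under zero effect after discontinuation when no imputation had imposed it.

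**Working it through.** **Inputs from the documents.** The assumed difference "is -2 days, and the standard deviation is 5.5 days"; the power calculation allows for multiplicity "by testing each dose versus placebo at a 0.025 significance level, 2-sided"; and "A total sample size of 250 participants will be randomized per treatment group and that will provide at least 96% power" (all Protocol 7.6). The between-month correlation rho, the covariance shape and the dropout rate are not given. Values for them below are assumptions.

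**1. The plan's own figure.** SE = 5.5 x sqrt(2/250) = 0.492. Then 2/0.492 = 4.07, the critical value is 2.24, and power is Phi(4.07 - 2.24) = 96.6%, against the stated 96%. It reproduces. The plan gives no figure for the copy-reference analysis itself.

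**2. What copy reference imputes.** With placebo mean mu_P and placebo covariance S, split into observed (o) and missing (m) months:

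E(Y_m | Y_o) = mu_P,m + S_mo S_oo^-1 (Y_o - mu_P,o)

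Averaged over atogepant dropouts whose observed months carry the effect d, the imputed difference from placebo is S_mo S_oo^-1 d. With zero correlation between months it is zero. With positive correlation it is not. Jump-to-reference replaces mu_P,o in the residual by the participant's own arm mean. That residual averages zero when dropout is unrelated to response, so the imputed difference is then zero.

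**3. Share of the earlier effect retained** (constant effect, equal monthly variances). Under compound symmetry it is rho after month 1 and 2rho/(1+rho) after month 2. Under AR(1) with month 1 the last observed, it is rho at month 2 and rho squared at month 3. If baseline is in the imputation model, rho is the correlation given baseline.

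| rho | Compound symmetry, after month 1 | Compound symmetry, after month 2 | AR(1), month 3 after month 1 |
|---|---|---|---|
| 0.3 | 30% | 46% | 9% |
| 0.5 | 50% | 67% | 25% |
| 0.7 | 70% | 82% | 49% |
| 0.8 | 80% | 89% | 64% |

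Under compound symmetry the share exceeds half only if rho > 0.5 after month 1. After month 2 the condition is 2rho/(1+rho) > 1/2, which gives rho > 1/3.

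**4. Effect on the 12-week difference**, with a fraction f of the active arm lost.

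- All lost after month 1, rho 0.75. Zero effect: -2(1 - 2f/3). Copy reference: -2[1 - (2f/3)(1 - 0.75)].
- Lost evenly after months 1 and 2, rho 0.7. Zero effect: -2(1 - f/2). Copy reference: -2[1 - f(0.5 x 2/3 x 0.3 + 0.5 x 1/3 x 0.176)] = -2(1 - 0.129f).

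| Pattern | f | Zero effect | Copy reference | Gap (days) |
|---|---|---|---|---|
| All after month 1 | 10% | -1.87 | -1.97 | 0.10 |
| All after month 1 | 20% | -1.73 | -1.93 | 0.20 |
| Even split | 10% | -1.90 | -1.97 | 0.07 |
| Even split | 20% | -1.80 | -1.95 | 0.15 |

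In the even-split pattern copy reference applies 0.129/0.5 = 26% of the zero-effect penalty at rho 0.7. The same calculation gives 65% at rho 0.3, 44% at 0.5 and 17% at 0.8.

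**5. Against the planned precision.** The least favourable value in the table, -1.73, is 1.73/0.492 = 3.5 standard errors, beyond the 2.24 needed. This uses the planned SE and adds nothing for imputation variance.

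**The case against.** The SAP is clear enough to program from. The protocol defers details to it, and it does not repeat the disputed sentence. That stands, so the fault lies in the stated assumption and not in the code. The sentence is still live, because SAP 18.0 lists only the addition of health outcome endpoints as a change from the protocol.

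A reader might infer that copy reference keeps most of the earlier benefit and is far milder than stated. The documents do not support that as fact. The share retained depends on an unstated correlation and covariance shape: at rho 0.3 it is 30% after month 1, and under AR(1) with rho 0.7 it falls to 49% by month 3. Any ratio of penalties rests on the same assumptions, and the trial estimate moves little.

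A reader might also infer that nothing else tests loss of effect after stopping. That goes too far. The off-treatment MMRM is also a US sensitivity analysis (Protocol 7.3.1.1 and 7.4). Protocol 8.8.1 keeps most treatment discontinuers on the diary to Week 12, and their off-treatment data are used. It is only a partial complement. Follow-up data after a new preventive is started are excluded, and months still missing are left unimputed under MAR (SAP 10.3.2). The analysis that would have imputed those months from off-treatment participants has been withdrawn because some pattern groups were too small (SAP 10.3.2.1).

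Jump-to-reference is not neutral for every dropout mechanism either. If those who leave had no early benefit, copy reference imputes a mean difference of zero, while jump-to-reference imputes means worse than placebo: 0.75 x 2 = 1.5 days worse after month 1 at rho 0.75. That also stands and should be noted beside the new analysis.

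Finally, correcting one sentence would remove the contradiction without a new analysis. That is true, and the fix allows it.

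**Conclusion.** The point holds. The property that the protocol attributes to copy reference is not one the method has, unless months are uncorrelated or the dropouts had no earlier benefit to carry. Under compound symmetry and a constant effect, 30-80% of the effect is retained after month 1 and 46-89% after month 2, over an assumed rho of 0.3 to 0.8.

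At rho of about 0.7-0.75 and the planned effect, the trial estimate differs from a true zero-effect analysis by about 0.07-0.1 days at 10% dropout and 0.15-0.2 days at 20%. A reader might go on to infer that the primary result is at risk. At the planned effect that is unlikely. The primary analysis, the alpha allocation and the testing order are untouched.

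The change should still be made. In a pivotal trial the one US sensitivity analysis labelled MNAR should match the assumption it is said to test.

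**What to change.** Preferred: add a jump-to-reference run to SAP 10.2.1.1, and name it in Protocol 7.3.1.1 as the analysis that targets zero effect after discontinuation. Take post-discontinuation means from placebo and earlier residuals around the participant's own arm mean, with the same 100 imputations, ANCOVA and Rubin pooling. State that it gives a zero mean difference when dropout is unrelated to response. Keep copy reference, labelled as the milder variant.

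Alternative, if only copy reference is kept: replace the protocol's sentence with a statement that a correlation-weighted share of the effect before discontinuation is retained through the placebo covariance.

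The first option costs one more imputation run, some wording, and a sensitivity estimate that is slightly less favourable under the assumptions above. The second costs one sentence.
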